9.3 Overdose

An overdose is defined as the accidental or intentional administration of any dose of a product that is considered both excessive and medically important.

All occurrences of overdose must be reported as SAEs (see Appendix 3).

In the event of an overdose the investigator/treating physician should:

- 1) Contact the BMS Medical Monitor/designee immediately
- 2) Closely monitor the participant for AEs/SAEs and laboratory abnormalities
- 3) Document the quantity of the excess dose as well as the duration of the overdosing in the CRF.

Decisions regarding dose interruptions or modifications will be made by the investigator in consultation with the BMS Medical Monitor/designee based on the clinical evaluation of the participant.

9.4 Safety

Planned time points for all safety assessments are listed in the Schedule of Activities. Safety assessments include AEs, physical examinations, vital signs, performance status, assessment of signs and symptoms, laboratory tests, and pregnancy tests as outlined in the Schedule of Activities.

9.4.1 Physical Examinations

Refer to Schedule of Activities, [Section 2](#).

9.4.2 Vital Signs

Refer to Schedule of Activities, [Section 2](#).

9.4.3 Electrocardiograms

Refer to Schedule of Activities, [Section 2](#).

9.4.4 Clinical Safety Laboratory Assessments

Laboratory assessments are listed in Table 9.4.4-1.

- Investigators must document their review of each laboratory safety report.
- All clinical safety laboratory assessments will be performed locally per the Schedule of Activities ([Section 2](#))

Table 9.4.4-1: Laboratory Assessment Panels

Hematology	
Hemoglobin	
Hematocrit	
Total leukocyte count, including differential	
Platelet count	
Serum Chemistry	
Aspartate aminotransferase (AST)	Albumin
Alanine aminotransferase (ALT)	Sodium
Total bilirubin	Potassium
Alkaline phosphatase	Chloride
Gamma-glutamyl transferase only when alkaline phosphatase is \geq Grade 2	Calcium
Creatinine	Phosphorus
Blood urea nitrogen (BUN) or serum urea level	Magnesium
Glucose	TSH, free T3 and free T4 - screening only
Lactate dehydrogenase (LDH)	TSH, with reflexive free T3 and free T4 if TSH is abnormal - on treatment
Uric acid	Creatinine clearance (CrCl) - screening only
	FSH (if needed to document postmenopausal status as defined in Appendix 4) - screening only
Troponin (local standard to be used/allowed), Cardiac Troponin T (cTnt), or I (cTnI): For those participants receiving ongoing treatment with relatlimab, troponin elevations will require the participant to undergo a cardiac	

Table 9.4.4-1: Laboratory Assessment Panels

evaluation. Following this evaluation, determination of further treatment will be based on the discretion of the Investigator.
Urinalysis
Protein
Glucose
Blood
Leukocyte esterase or leukocyte
Specific gravity
pH
Serology (at screening)
Serum for hepatitis C antibody (if Hepatitis C antibody is positive reflex to hepatitis C RNA) or hepatitis C RNA, hepatitis B surface antigen, HIV-1 and HIV-2 antibodies. (Testing for HIV-1 and HIV-2 must be performed at sites where mandated by local requirements, see Appendix 8)
Other Analyses
Pregnancy test (WOCBP only, Section 2).

9.4.5 Imaging Safety Assessment

Any incidental findings of potential clinical relevance that are not directly associated with the objectives of the protocol should be evaluated and handled by the study investigator per standard medical/clinical judgment.

9.5 Pharmacokinetic and Immunogenicity Assessments

Serum samples for relatlimab and nivolumab PK and ADA assessments will be collected for all subjects.

9.5.1 Pharmacokinetics: Collection and Processing

A detailed schedule of PK and ADA evaluations is provided in [Table 9.5.1-1](#). All time points are relative to the start of study drug administration. Pre-dose samples should be taken within 30 minutes before the start of dose administration. If samples are drawn but study drug(s) is not administered on the same day, samples will be retained and analyzed as planned. There is no need to collect another sample when dosing is resumed. End-of-infusion samples should be taken just prior to the end of infusion (preferably within 2 minutes). Further details of sample collection, processing, and shipment will be provided in the laboratory procedures manual. On treatment PK samples are intended to be drawn relative to actual dosing days, if a dose occurs on a different day within the cycle due to delays or minor schedule adjustments, PK samples should be adjusted accordingly.

Table 9.5.1-1: PK and ADA Sampling Schedule for Relatlimab and Nivolumab

Study Day of Sample Collection (1 Cycle = 4 Weeks)	Event (Relative to Study Treatment Dosing)	Time (hour:min) (Relative to Start of Dose Administration)	Pharmacokinetics (2 Distinct Samples)	Anti-Drug Antibodies (2 Distinct Samples)
Cycle 1 Day 1	Predose ^a		X	X
Cycle 1 Day 1	End of infusion ^b	01:00 ^b	X	
Cycle 2 Day 1	Predose ^a		X	X
Cycle 6 Day 1	Predose ^a		X	X
Cycle 6 Day 1	End of infusion ^b	01:00 ^b	X	
Every 4th Dose After Cycle 6				
Day 1	Predose ^a		X	X
End of Treatment and Follow-Up Period				
Follow-Up Visit 1			X	X
Follow-Up Visit 2			X	X

^a Take all predose samples for nivolumab prior to the start of nivolumab infusion.

^b Since the end of infusion-PK (EOI-PK) sample is drawn with the intent of accurately estimating the maximum concentration (C_{max}) of the drug, draw the EOI-PK when all the study drug has been infused. If the site infuses drug without a flush, then collect the EOI-PK sample within approximately 5 minutes after end of infusion. If a flush is administered to clear the IV lines of the drug and to ensure delivery of the entire drug dose, then draw the EOI-PK sample within approximately 5 minutes after end of the flush. Do not draw EOI samples from the same IV access that the drug was administered.

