- d) WOCBP must agree to follow instructions for method(s) of contraception (see [Appendix 4](#)) for the duration of treatment with study treatment(s) plus 24 weeks after the last dose of study treatment (ie, 30 days [duration of ovulatory cycle] plus the time required for nivolumab and relatlimab to undergo approximately 5 half-lives).
- e) Males who are sexually active with WOCBP must agree to follow instructions for method(s) of contraception (see [Appendix 4](#)) for the duration of treatment with study treatment(s) plus 33 weeks after the last dose of the study treatment (ie, 90 days [duration of sperm turnover] plus the time required for nivolumab and relatlimab to undergo approximately 5 half-lives). In addition, male participants must be willing to refrain from sperm donation during this time.
- f) WOCBP who are continuously not heterosexually active are exempt from contraceptive requirements, and still must undergo pregnancy testing as described in this section.

Investigators shall counsel WOCBP, and male participants who are sexually active with WOCBP, on the importance of pregnancy prevention and the implications of an unexpected pregnancy. Investigators shall advise on the use of highly effective methods of contraception ([Appendix 4](#)) which have a failure rate of < 1% when used consistently and correctly.

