7.1.1 BMS-986213 or Nivolumab Dosing

BMS-986213 (prepared in normal saline for relatlimab 160 mg/nivolumab 480 mg) or nivolumab 480 mg dosing is to be administered as an IV infusion through a 0.2-micron to 1.2-micron pore-size, low-protein binding in-line filter at the protocol-specified doses. It is not to be administered as an IV push or bolus injection. Instructions for dilution and infusion of relatlimab/nivolumab or nivolumab injection will be provided in the pharmacy binder. Care must be taken to assure sterility of the prepared solution as the product does not contain any antimicrobial preservative or bacteriostatic agent.

Participants should receive BMS-986213 or nivolumab as a 1-hour infusion on Day 1 of each treatment cycle until progression, unacceptable toxicity, withdrawal of consent, or the study ends,

whichever occurs first. Participants should begin study treatment within 3 calendar days of randomization.

The sponsor, participants, investigator, and site staff will be blinded to the study drug administered. Each investigative site must assign an unblinded pharmacist/designee.

There will be no dose escalations or reductions of any study treatment allowed. Participants may be dosed within a ± 3 day window (ie, participants may be dosed no less than 25 days and no more than 31 days between doses). Premedication is not recommended for the first dose of either treatment.

Participants should be carefully monitored for infusion reactions during administration. If an acute infusion reaction is noted, participants should be managed according to [Section 7.7.3](#).

Doses may be interrupted, delayed, or discontinued depending on how well the participant tolerates the treatment. Dosing visits must not be skipped, only delayed.

Infusions are compatible with polyvinyl chloride (PVC) or polyolefin containers and infusion sets, and glass bottles.

Care must be taken to assure sterility of the prepared solution as the product does not contain any antimicrobial preservative or bacteriostatic agent.

For details on prepared drug storage, preparation, and administration, please refer to the IBs and/or pharmacy binder.

The selection and timing of dose for each participant is provided in [Table 7.1-1](#).

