10.2.4.1 Pharmacokinetic Analyses

Trough concentrations of relatlimab will be plotted versus study day and cycle. Nivolumab end-of-infusion and trough (C_{trough}) concentrations will be tabulated using summary statistics. These data may also be pooled with other datasets for population PK analysis which will be presented in a separate report.

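### Section 9.5.1 of the protocol times the end-of-infusion PK sample before the infusion ends in its text and after the whole dose is in under footnote b, so Ceoi summaries can mix the two (minor inconsistency)

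*Protocol*

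**What the plan says.** Protocol Section 9.5.1 deals with the end-of-infusion (EOI) sample twice.

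- **Body text:** "End-of-infusion samples should be taken just prior to the end of infusion (preferably within 2 minutes".
- **Table 9.5.1-1, footnote b:** the sample is "drawn with the intent of accurately estimating the maximum concentration", and sites should "draw the EOI-PK when all the study drug has been infused". Without a flush, "then collect the EOI-PK sample within approximately 5 minutes after end of infusion". With a flush, "then draw the EOI-PK sample within approximately 5 minutes after end of the flush".

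Footnote b is attached to both EOI rows in the table, Cycle 1 Day 1 and Cycle 6 Day 1. No other section says which instruction governs. Further collection detail is left to a laboratory procedures manual that is not among the documents.

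The results are planned outputs. Protocol Section 10.2.4.1 says that nivolumab end-of-infusion and trough "concentrations will be tabulated using summary statistics". SAP Section 7.7.2 tabulates, lists and plots Ceoi by cycle and study day. Neither section says how the actual sampling time is handled.

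**The concern.** A sample drawn before the infusion ends reflects a dose that is not yet fully delivered. A sample drawn after the infusion or flush reflects the full dose. The first does not serve the purpose that footnote b states, which is to estimate Cmax. With both instructions in force and no analysis rule on sampling time, values of both kinds could be reported under one label. At stake are the level of the Ceoi summary, which early draws would pull down, and some added spread between sites.

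**Working it through.** **1. The two instructions side by side**

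| Source | Timing relative to end of infusion | Dose delivered at the draw |
|---|---|---|
| Section 9.5.1 text | Before the end, preferably within 2 minutes of it | Incomplete |
| Footnote b, no flush | 0 to about 5 minutes after | Complete |
| Footnote b, flush used | 0 to about 5 minutes after the flush ends (flush length not stated) | Complete |

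The text and the footnote do not overlap, so no draw time satisfies both. The plan gives no figure for the effect, so there is none to reproduce. The steps below size it.

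**2. Inputs**

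- Infusion length is 60 minutes. Protocol Section 7.1.1: "Participants should receive BMS-986213 or nivolumab as a 1-hour infusion on Day 1 of each treatment cycle".
- The dosing interval is 28 days (Q4W).
- Half-life is an assumption, implied by Protocol Section 6.1, which sets contraception at "24 weeks after the last dose of study treatment (ie, 30 days [duration of ovulatory cycle] plus the time required for nivolumab and relatlimab" to pass about 5 half-lives. That gives (24 × 7 − 30)/5 = 138/5 = 27.6 days. The 33-week male window in the same section gives (33 × 7 − 90)/5 = 141/5 = 28.2 days.
- The model is one compartment with a constant-rate infusion.

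**3. Cycle 1.** Elimination within the hour is negligible, so concentration during the infusion is close to proportional to the dose delivered.

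- C(58 min)/C(60 min) = 58/60 = 0.967, which is 3.3% low.
- Decline from 60 to 65 minutes: exp(−ln 2 × 5/(27.6 × 1440)) = 0.99991, or about 0.01%.
- C(58)/C(65) is therefore also 0.967.

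The shortfall comes almost entirely from the minutes before the end of infusion. The minutes after it contribute next to nothing.

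**4. Cycle 6.** Drug carried over from five earlier doses dilutes the shortfall.

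- Fraction remaining after 28 days: r = 2^(−28/27.6) = 0.495.
- Accumulation over six doses: (1 − r^6)/(1 − r) = (1 − 0.0147)/0.505 = 1.95.
- Shortfall: 0.0333/1.95 = 0.017, which is 1.7% low. The full model gives C(58)/C(65) = 0.983.

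**5. Sensitivity.** To allow for faster early decline, the half-life was varied from 0.25 to 28.2 days. C(58)/C(65) then ran from 0.967 to 0.983, so the 58-minute sample is 1.7% to 3.3% low throughout. At 0.25 days it is 2.2% low at both cycles.

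**6. What could enlarge it.** The 2 minutes is only a preference. Each further minute early adds 1/60, about 1.7 percentage points, at Cycle 1, and 1/(60 × 1.95), about 0.9 points, at Cycle 6. Drug left in the line would add to this, but its volume is not stated and cannot be sized.

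**The case against.** The best defence is that sites may in practice follow only one rule. Footnote b is the more specific instruction, gives its reason and is attached to both EOI rows. The Revised Protocol 03 summary of changes says the footnotes were updated to clarify EOI collection in relation to the flush. That suggests the body sentence was simply not brought into line. The laboratory manual may also settle the matter. This stands in part: it limits the consequence to a possibility, but it does not remove the contradiction from the current protocol text.

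Four stronger readings are tempting, and the documents do not support them.

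- **A reader might infer that Ceoi does mix two quantities.** Mixing occurs only if sites follow different instructions, and nothing in the documents shows that they did.
- **A reader might add 2 minutes before to 5 minutes after and treat a 7-minute spread as the source of the error.** Under the half-life implied by the protocol, the 5 minutes after the end change the concentration by about 0.01%.
- **A reader might infer that the population PK model is compromised.** Protocol Section 10.2.4.1 and SAP Sections 4.3.1 and 7.7.1 say only that the data may be pooled, and SAP Section 7.7.3 makes the analysis conditional on need. A model using actual sampling times would absorb most of the difference, although the SAP does not state that it will use them.
- **A reader might infer bias between arms.** Both blinded arms have the same infusion length and the same sampling rules, so no differential effect is shown.

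A further fair point is that a protocol edit acts only on future draws. SAP Section 5.2.1 dates the final PFS analysis to 09 March 2021, and SAP version 5.0 is dated 25 October 2021. With EOI draws only at Cycles 1 and 6, most have probably been taken already.

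**Conclusion.** The point holds as a minor internal inconsistency that is wrong as written. The body text and footnote b cannot both be followed, and the body-text timing defeats the stated purpose of the sample. If sites differ, the Ceoi summaries can combine incomplete-dose and complete-dose values. A draw 2 minutes early reads about 3.3% low at Cycle 1 and about 1.7% low at Cycle 6. These sizes rest on a one-compartment model, a 60-minute infusion, and a half-life inferred from the contraception window and not reported as such. Earlier draws or residual drug in the line would increase them. PK is an exploratory objective in both phases (Protocol Table 4-1). Trough concentrations, hypothesis tests, and the efficacy and safety analyses are unaffected.

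**What to change.** 1. **Protocol Section 9.5.1:** replace the body sentence on EOI timing with a reference to footnote b of Table 9.5.1-1, which carries the rationale. Check that the laboratory manual agrees.
2. **SAP Section 7.7.2:** for samples already drawn, add one sentence stating that Ceoi is summarised using actual sampling times, and that samples drawn before the end of infusion are flagged or excluded from the Ceoi summary.

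The cost is one sentence in each document, with no change to sample size, visits or any confirmatory analysis. The SAP step assumes that actual draw times and infusion stop times were recorded, which should be confirmed.

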9.5.2 Pharmacokinetic Sample Analyses

The serum samples will be analyzed for relatlimab and nivolumab by a validated immunoassay. Samples collected from a participant in the nivolumab monotherapy group may not be analyzed for relatlimab concentrations. In addition, selected serum samples may be analyzed by an exploratory orthogonal method (eg, liquid chromatography [LC]-mass spectrometry [MS]/MS) that measures total relatlimab and/or nivolumab, but the generated data will not be reported. Only results generated from the validated immunoassay method will be reported. Potential results generated from any orthogonal method are intended as informational for technology exploration purposes and will not be reported.

For adolescent participants, local standards for volumes of blood based on body weight that may be drawn within a specific time period should be followed. In order to obtain the samples required for safety, PK, and PD evaluations specified at a time point, blood volumes for safety laboratory

analysis should be minimized through the use of pediatric sample tubes, if possible. If, despite the use of these measures, the blood volumes required in the Schedule of Activities for a time point will exceed those recommended for the participant, the sponsor should be contacted for instructions on which blood tests can be omitted or modified to meet volume requirements. These omitted/modified tests will likely be for pharmacodynamic and/or pharmacokinetic assessments, since all required safety assessments must be performed.

9.5.3 Immunogenicity

Serum samples for analysis of development of ADAs will be collected in conjunction with analysis of relatlimab and nivolumab serum concentrations and will be collected from all participants as indicated in [Table 9.5.1-1](#). These serum samples will be analyzed for relatlimab and nivolumab ADAs by a validated immunoassay; samples may also be analyzed for neutralizing antibodies by validated methods. Samples collected from a participant in the nivolumab monotherapy group may not be analyzed for relatlimab ADAs. Selected serum samples may be analyzed by an exploratory orthogonal method that measures anti-relatlimab or anti-nivolumab antibodies. Potential results generated from any orthogonal method are intended as informational for technology exploration purposes and will not be reported. In addition, serum samples designated for PK or biomarker assessments may also be used for immunogenicity analysis if required (eg, insufficient volume for complete immunogenicity assessment or to follow up on suspected immunogenicity related AE). Further details of blood collection and processing will be provided to the site in the procedure manual.

9.6 Pharmacodynamics

PD analysis will be performed on serum, plasma, peripheral blood RNA, and/or peripheral blood mononuclear samples collected at time points specified in [Table 9.8.2.6-1](#). The purpose of these exploratory analyses will be to identify PD markers changing with treatment, including changes that are associated with clinical benefit.

9.7 Pharmacogenomics

Pharmacogenomics assessments include, gene expression profiling, and mutational analyses as described in further detail in Section 9.8.

9.8 Biomarkers

Peripheral blood and tumor tissue will be collected prior to therapy. Peripheral blood samples will also be collected at selected time points on treatment. If a biopsy or surgical resection is performed at the time of progression or suspected progression, tumor sample (block or slides) should be submitted for analysis. If biomarker samples are drawn but study drug(s) is not administered, samples will be retained. A detailed description of each assay system is described below and a schedule of pharmacodynamic evaluations is provided in [Table 9.8.2.6-1](#). All biomarker sampling at time points when study drug is not administered are optional.

9.8.1 Peripheral Blood Markers

A variety of factors that may impact the immunomodulatory properties and efficacy of relatlimab in combination with nivolumab will be investigated in peripheral blood specimens taken from all

subjects prior to or during treatment. Data from these investigations will be evaluated for associations with response, survival, and/or safety (AE) data. Several analyses will be completed and are described briefly below.

9.8.1.1 Soluble Biomarkers

Soluble factors, such as cytokines, chemokines, soluble receptors, and antibodies to tumor antigens will be characterized and quantified by immunoassays in serum. Analyses may include, but not necessarily be limited to, soluble LAG-3, CXCL-9 and IL2Ralpha. Collected serum samples may also be used for the assessment of tumor antigen-specific responses elicited following treatment with monotherapy and combination therapy to explore which antitumor antibodies are most associated with clinical response. Antibody levels to cancer test antigens may be assessed by multiplex assays and enzyme-linked immunosorbent assay (ELISA).

9.8.1.2 Immunophenotyping

The proportion of specific lymphocyte subsets and expression levels of T cell co-stimulatory markers in peripheral blood mononuclear cell (PBMC) preparations will be quantified by flow cytometry. Analyses may include, but not necessarily be limited to, the proportion of T, B, and NK cells, granulocytes, the proportion of memory and effector T cell subsets, and expression levels of PD-1, PD-L1, other B7 family members, ICOS, and Ki67.

9.8.1.3 T-Cell Repertoire Analysis

Low diversity of the peripheral T-cell compartment has been shown to correlate with poor overall survival in metastatic breast cancer. A standing theory in immuno-oncology suggests a diverse and activated immune environment is better adept at eradicating tumor compared to a skewed repertoire of naïve and tolerized T cells. In order to explore whether a diverse T-cell repertoire is predictive of response to therapy, DNA/RNA sequencing will be performed on DNA/RNA isolated from peripheral blood and tumor tissue ([Section 9.8.2.3](#)) to quantitate the composition of the T-cell repertoire prior to and during therapy.

9.8.1.4 Whole Blood for Germline DNA

Whole blood will be collected from all subjects prior to treatment to generate genomic DNA for genetic analyses and to serve as a reference for tumor genomic testing. These analyses will focus on, but are not limited to, genetic variations within genes associated with PD1 and other immunoregulatory signaling pathways to determine if natural variation within those genes is associated with response to nivolumab and/or with adverse events during treatment.

